4.2 Analysis Sets

4.2.1 Intent-to-Treat Population (ITT)

The Intent-to-Treat (ITT) population will include all patients who are randomized via the IWRS. All efficacy analyses, including the primary analysis, will be performed on the ITT population. Patients will be analysed according to the randomized treatment.

4.2.2 Modified Intent-to-Treat Population (mITT)

The Modified Intent-to-Treat (mITT) population will include all randomized patients who have study drug dispensed after randomization. Groups will be defined based on the randomized treatment.

4.2.3 Per Protocol Population (PP)

The Per-Protocol (PP) population will include all mITT patients without any major protocol deviations, and who had $\geq 80\%$ compliance while on treatment. To be included in the PP population the minimum time on therapy is 90 days.

4.2.4 Safety Population

All safety analyses will be conducted based on the Safety population, which is defined as all randomized patients. This is the same as the ITT population.

4.3 Statistical Considerations

4.3.1 General Statistical Considerations

All statistical analyses and data summaries are to be generated according to this SAP. Any deviations from this SAP will be documented in the CSR.

All null hypotheses will be defined as no treatment difference. All statistical tests for the efficacy outcomes will be performed at the two-sided 5% significance level, unless otherwise noted. The iSAP will utilize one-sided testing for efficacy at the 0.025 level for interim analyses, the operating characteristics of which are identical to those of a corresponding group sequential design with a two-sided alpha level of 0.05.

Summary statistics will be presented by treatment group and by visit where appropriate. Data will be presented “as-observed”, unless otherwise specified. Continuous data will be summarized with descriptive statistics: count (n), number of missing values (n-missing), mean, standard deviation (SD), median, minimum, and maximum. Categorical data will be described using frequencies and percentages, including a category for missing values where appropriate. Percentages are based on the number of patients in the analysis set. All meaningful patient data collected in the database will be listed. Listings will be sorted by patient within center/site.

4.3.2 Missing Data

Only measurements obtained at each study visit will be used in presenting tabular data summaries, unless otherwise stated. Unless otherwise stated, observed data will be presented in tables and listings without imputation of missing values. All measurements, including unscheduled or repeated assessments, will be presented in data listings.

Medications, except study drug, with missing stop dates will be considered in concurrent use with study drug during the study period and counted in the summary table of concomitant medications unless the start date of the medication was after study completion or after discontinuation from study.

Adverse events with missing onset dates will be considered treatment-emergent for randomized patients if the adverse event stop date is after randomization. Adverse events with missing stop dates will be considered treatment-emergent for randomized patients. If only the year is present for AE stop dates, then December 31 will be used as the month and day, respectively. If only the day is missing, the first of the month will be used for all start dates and the last day of the month will be used for all end dates.

Missing AE relationship will be presented as ‘related’ in tables and missing in listings. In addition, tables that describe the collected data and that include a ‘missing’ relationship category where appropriate will be presented. Missing AE intensity/severity will be presented in a ‘missing’ category in tables and as missing in listings.

Event or censoring dates used in the time-to-event analysis of efficacy endpoints will be imputed to the first of the month only if the day is missing and the month and year are both known. However, for events that occurred in the same month as randomization, the day will be imputed as the date of randomization. For event or censoring with missing months or years, the event or censoring date will be imputed to the last known date without a previous event, or January 1 if only year is known, whichever is later.

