4.8.1 Adverse Events

AEs are recorded from the time the informed consent is signed until study participation is complete. Adverse events with onset on or after the date of dispensing study drug for each patient will be considered treatment-emergent (TEAEs). This will include any AE with onset prior to initiation of study drug and increased severity after the treatment initiation.

By design of this study, serious AEs (SAEs) that are endpoint events will only be recorded for the endpoint determination and not captured as SAEs. Following adjudication, if the event is determined to not meet the criteria for an event, the event will be evaluated as an SAE.

Adverse events will be coded using the most recent available Medical Dictionary for Regulatory Activities (MedDRA) Version. Coding includes system organ class (SOC) and preferred term (PT). All AEs will be listed by patient and by SOC and PT; these listings will present detailed information concerning adverse events, including the verbatim description, time of onset and resolution, severity, relationship to study drug, action taken, and outcome.

Pre-treatment AEs:

Pre-treatment-emergent AEs will be defined as any AE that started before the patient's randomization. (An AE that was ongoing at the time of randomization and subsequently increased in severity is also considered treatment-emergent.) Pre-treatment AEs will be listed separately from TEAEs.

Treatment-emergent AEs:

For each patient, the following AEs will be defined as TEAEs:

- AEs occurring after randomization;
- AEs occurring within 30 days after the completion or withdrawal from study;
- AEs started prior to randomization but worsened in severity following randomization;
- AEs with partial onset dates if the AE stop date is after randomization and the dates do not definitively place the AE start date before randomization; and
- AEs with completely missing onset dates.

The frequency and percentage of patients with any TEAEs will be summarized. TEAEs will be presented by SOC and PT. At each summary level, a patient will be counted only once for each TEAE he/she experiences within that level, regardless of how many occurrences of that TEAE that patient experienced. The percentage of patients having had at least one TEAE at each level will be calculated.

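### SAP 4.3.2 counts every adverse event without a stop date as treatment-emergent, which contradicts SAP 4.8.1 and protocol 12.2.5 for events known to have begun before randomization

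*Combined protocol and SAP*

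**What the plan says.** Two SAP sections assign treatment-emergent status.

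SAP 4.3.2 works from missing dates. For onset: "Adverse events with missing onset dates will be considered treatment-emergent for randomized patients if the adverse event stop date is after randomization". For the stop date: "Adverse events with missing stop dates will be considered treatment-emergent for randomized patients". The second rule neither looks at onset nor separates an ongoing event from one whose end is unknown. For partial dates: "If only the day is missing, the first of the month will be used for all start dates". The paragraph on efficacy dates makes an exception for the month of randomization ("However, for events that occurred in the same month as randomization, the day will be imputed as the date of randomization"); the adverse event paragraph has none.

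SAP 4.8.1 defines the tables. "Pre-treatment-emergent AEs will be defined as any AE that started before the patient's randomization", and "Pre-treatment AEs will be listed separately from TEAEs". An earlier onset becomes treatment-emergent only under the entry "AEs started prior to randomization but worsened in severity following randomization". A partial onset date counts as treatment-emergent if the event stopped after randomization and the dates do not definitively put onset earlier. A completely missing onset date always counts.

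Protocol 12.2.5 agrees with 4.8.1: new onset once study drug has started, or earlier onset with increased severity.

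**The concern.** A missing stop date carries no information about when an event began. Under 4.3.2 as worded, an event with a fully known onset during screening enters the treatment-emergent tables merely because nobody recorded its end. Under 4.8.1 the same record belongs in the separate pre-treatment listing. SAP 4.3.1 requires all analyses to follow the SAP, and no sentence ranks the two sections, so a programmer cannot satisfy both. At stake are the content of the treatment-emergent tables and whether two programmers would reproduce the same ones. Efficacy, alpha and sample size are untouched.

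**Working it through.** The plan states no figure on this point, so the check sets the rules side by side for each type of record. No worsening in severity is assumed throughout.

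| Record | SAP 4.3.2 | SAP 4.8.1 |
|---|---|---|
| A. Known onset before randomization, no stop date | treatment-emergent | pre-treatment |
| B. No onset date, stopped before randomization | condition not met, so not treatment-emergent | treatment-emergent |
| C. No onset date, no stop date | treatment-emergent | treatment-emergent |
| D. Onset day missing, month of randomization, no stop date | treatment-emergent | not settled: its partial-onset entry asks for a stop date after randomization |
| E. Onset day missing, month of randomization, stopped after randomization | start set to the 1st | treatment-emergent |

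**Record A.** All such events are treatment-emergent under 4.3.2 and none under 4.8.1. Protocol 12.2.5 sides with 4.8.1.

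**Record B.** The conflict runs the other way. An event that ended before randomization must also have begun before it, so here 4.3.2 gives the sensible answer.

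**Records C and D.** Here the missing-stop-date rule does useful work, so deleting it would be the wrong remedy.

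**Record E.** Apply 4.3.2 alone and count the pairs of randomization day and onset day in the same month, with onset on or after randomization, over a 365-day year.

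- A month of n days gives n(n+1)/2 pairs: 7 × 496 + 4 × 465 + 406 = 5738.
- The imputed 1st falls before randomization unless randomization was itself on the 1st, which accounts for 365 pairs.
- 5738 − 365 = 5373, and 5373/5738 = 93.6%.

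This counts calendar combinations and does not estimate how often such records occur. Under the 4.8.1 partial-onset entry these events come back, because an unknown day within the month of randomization does not definitively place onset earlier. What remains is an event that starts and stops on the day of randomization, whose stop date is not after randomization.

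**How many records of type A are possible.** Protocol 10.2 and SAP 4.8.1 collect adverse events from consent. Protocol 6.1.1.1 allows 42 days from Visit 1 to randomization, and 6.1.1.2 allows 60 when there is a Visit 1.1. Protocol 10.2 excludes conditions present at screening or baseline that do not deteriorate. That leaves new events arising in this window, unworsened and without a stop date. The documents give no count of them.

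**The case against.** The best defence is that the sentence in 4.3.2 directly follows the missing-onset rule and may be meant to complete it: if the stop date is missing as well, count the event. That reading fits 4.8.1, which is the section that defines the tables and which keeps pre-randomization events in their own listing. On this view there is a loose sentence and no real contradiction. The defence can add that protocol 10.2 and the schedule of procedures start active adverse event assessment at Visit 2, so few screening events will be recorded, and that SAP 4.8 plans no formal comparison of safety data. The iSAP (4.1) does show p-values for adverse events at the interims, but only as flags.

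Most of this stands as an argument about size. It does not rescue the wording. The sentence covers every event with a missing stop date, and nothing ties it to the sentence before it. The SAP plans a separate listing of pre-randomization events, so its authors expected some. The defence also leaves record B unresolved.

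**Conclusion.** Wrong as written, minor. SAP 4.3.2 contradicts SAP 4.8.1 and protocol 12.2.5 for events with known onset before randomization, no worsening and no stop date. It also conflicts with 4.8.1 for events with no onset date that stopped before randomization. Following 4.3.2 literally would over-count treatment-emergent events in the first group. The rule applies alike to both arms, and the number affected cannot be derived from the documents.

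A reader might infer three stronger things that the documents do not support.

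- **That first-of-month imputation drops true treatment-emergent events from the tables.** This happens only if 4.3.2 is applied alone or if imputed dates override 4.8.1. What is left is an ambiguity: the SAP does not say whether imputed dates feed the classification.
- **That chronic pre-existing conditions swell the tables.** Protocol 10.2 keeps stable ones from being reported as adverse events at all.
- **That the over-count dilutes a risk ratio by a calculable amount.** Any such figure would be pure assumption, since no frequency is given and 4.8.1 plans counts and percentages, not ratios.

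**What to change.** Amend SAP 4.3.2 as follows.

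1. Limit the missing-stop-date sentence to events whose onset date is missing, or partial and not definitively before randomization. Limiting it to events with both dates missing would leave record D uncovered.
2. State that treatment-emergent status follows 4.8.1, using the dates as collected and not as imputed, with one exception: an event with a missing onset date and a stop date before randomization is pre-treatment. Without the exception, deferring to 4.8.1 would count record B as treatment-emergent.
3. If imputed start dates are used for this status after all, set a day-missing start to the randomization date only when its month and year are those of randomization and the stop date is not before randomization. Without the month limit, an event with onset in May, randomization on 10 June and a stop in July would be moved to 10 June and wrongly become treatment-emergent.

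The cost is a few sentences in the SAP and the matching lines in the derivation of the treatment-emergent flag. No data collection or efficacy analysis changes.

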4.3.3 Baseline

In general, the baseline value will be defined as the last non-missing measurement obtained prior to the dispensing drug, unless otherwise specified. If the baseline value is missing, the value obtained at the screening visit will be used as the baseline value.

Lipid, lipoprotein, and inflammatory marker baseline values will be derived variables. LDL-C may be obtained by various methods at each visit; therefore, the baseline value obtained via Preparative Ultracentrifugation will be used, unless this value is missing. If the LDL-C Preparative Ultracentrifugation value is missing, then another LDL-C value will be used, with prioritization of values obtained from LDL-C Direct measurements, followed by LDL-C derived by the Friedewald calculation (only for subjects with TG < 400 mg/dL), and finally LDL-C derived using the calculation published by Hopkins University investigators (Martin 2013). For all other lipid, lipoprotein, and inflammatory marker parameters, wherever possible, baseline will be derived as the arithmetic mean of the Visit 2 (Day 0) value and the preceding Visit 1 (or Visit 1.1) value. If only one of these values is available, the single available value will be used as baseline.

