6.3.1.2. Fasting Lipid Profile

The fasting lipid panel includes: TG, TC, LDL-C, HDL-C, non-HDL-C, and VLDL-C.

At all visits, LDL-C will be calculated using the Friedewald equation if TG <400 mg/dL. At Visit 1 and Visit 1.1 Direct LDL-C will be used if at the same visit TG >400 mg/dL (4.52 mmol/L). These LDL-C values will be used for the evaluation of the LDL-C inclusion

criteria (LDL-C qualifying measurements for randomization) and for the assessment of changes in the statin therapy when LDL-C is not at goal. At all remaining visits LDL-C will be measured by Direct LDL-C or by Preparative Ultracentrifugation if at the same visit TG >400 mg/dL (4.52 mmol/L). In addition, irrespective of the TG levels, at Visit 2 (0 Months of Follow-up, baseline) and at Visit 4 (12 Months of Follow-up), LDL-C direct and LDL-C Preparative Ultracentrifugation will be taken. These Preparative Ultracentrifugation LDL-C measurements will be used in the statistical analysis including the calculation of the percent change from baseline (1 year versus baseline). Hopkins LDL-C (Martin 2013) will be calculated for each visit.

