- Composite of CV death, nonfatal MI (including silent MI), non-elective coronary revascularizations (defined as emergent or urgent classifications), unstable angina determined to be caused by myocardial ischemia by invasive/non-invasive testing and requiring emergent hospitalization, nonfatal stroke, or PVD requiring intervention, such as angioplasty, bypass surgery, or aneurism repair;
- Composite of CV death, nonfatal MI (including silent MI), non-elective coronary revascularizations (defined as emergent or urgent classifications), unstable angina determined to be caused by myocardial ischemia by invasive/non-invasive testing and requiring emergent hospitalization, PVD requiring intervention, or cardiac arrhythmia requiring hospitalization of ≥ 24 hours;
- New CHF;
- New CHF as the primary cause of hospitalization;
- Transient ischemic attack (TIA);
- Amputation for PVD;
- Carotid revascularization;
- All coronary revascularizations defined as the composite of emergent, urgent, elective, or salvage;
- Emergent coronary revascularizations;
- Urgent coronary revascularizations;

- Elective coronary revascularizations;
- Salvage coronary revascularizations;
- Cardiac arrhythmias requiring hospitalization of ≥ 24 hours;
- Cardiac arrest;
- Ischemic stroke;
- Hemorrhagic stroke;
- Fatal or nonfatal stroke in the subset of patients with a history of stroke prior to baseline;
- New onset diabetes, defined as Type 2 diabetes newly diagnosed during the treatment/follow-up period;
- New onset hypertension, defined as blood pressure ≥ 140 mmHg systolic OR ≥ 90 mm Hg diastolic newly diagnosed during the treatment/follow-up period;
- Fasting TG, TC, LDL-C, HDL-C, non-HDL-C, VLDL-C, apo B, hs-CRP (hsCRP and $\log[\text{hsCRP}]$), hsTnT, and RLP-C (to be estimated from standard lipid panel, $\text{RLP-C} = \text{TC} - \text{HDL-C} - \text{LDL-C}$ [Varbo 2014]) (based on ITT estimands):
 - Assessment of the relationship between baseline biomarker values and treatment effects within the primary and key secondary composite endpoints,
 - Assessment of the effect of AMR101 on each marker,
 - Assessment of the relationship between post-baseline biomarker values and treatment effects within the primary and key secondary composite endpoints by including post-baseline biomarker values (for example, at 4 months, or at 1 year) as a covariate;
- Change in body weight;
- Change in waist circumference.

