For measurements of lipids, lipoproteins, and inflammatory markers, the change from baseline and the percent change will be summarized at each visit. Since these parameters are typically not normally distributed, the Wilcoxon rank-sum test will be used for treatment comparisons of the percent change from baseline, and medians and quartiles will be provided for each treatment group. The medians of the differences between the treatment groups and 95% CIs will be estimated with the Hodges-Lehman method. In addition, shift-tables may be generated as appropriate.

As an additional exploratory analysis, the relationship between post-baseline biomarker values and treatment effects with the primary and key secondary composite endpoints will be assessed by adding biomarker values (for example, at 4 month, or at 1 year, etc.) as time-dependent covariates in the Cox proportional hazards model. Diagnostic plots for the proportional hazards assumption will be evaluated.

Weight is measured at the screening visit and at all follow-up visits, including the last visit of the study. Waist circumference will be measured at the randomization visit (Visit 2; Day 0), Visit 5 (Day 720) and the last visit of the study. Descriptive statistics will be presented by visit and treatment group for baseline, post-treatment change from baseline, and the percent change from baseline. Analysis methods for repeated measurements will be used to compare percent change from baseline between treatments.

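### After Visit 4 the SAP's LDL-C change from baseline sets a calculated value against an ultracentrifugation baseline, which shifts the within-arm change by an unknown amount

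*Combined protocol and SAP*

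**What the plan says.** **Baseline.** SAP 4.3.3 notes that "LDL-C may be obtained by various methods at each visit" and therefore fixes one method at baseline: "the baseline value obtained via Preparative Ultracentrifugation will be used, unless this value is missing". If it is missing, the order is Direct LDL-C, then Friedewald (TG below 400 mg/dL only), then Hopkins.

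**Which method is run when.** Protocol 6.3.1.2 states: "At all visits, LDL-C will be calculated using the Friedewald equation if TG <400 mg/dL". It adds that "irrespective of the TG levels, at Visit 2 (0 Months of Follow-up, baseline) and at Visit 4 (12 Months of Follow-up), LDL-C direct" and ultracentrifugation are both taken. After screening, when TG is above 400 mg/dL: "At all remaining visits LDL-C will be measured by Direct LDL-C or by Preparative Ultracentrifugation if at the same visit". Hopkins LDL-C is calculated at every visit.

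**What is analysed.** SAP 3.2.1.3 lists "Assessment of the effect of AMR101 on each marker" as a tertiary endpoint, with LDL-C among the markers. For lipids, SAP 4.7.4 states that "the change from baseline and the percent change will be summarized at each visit", and it compares percent change between arms with the Wilcoxon rank-sum test.

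**Time points with their own LDL-C rule.** SAP 4.7.4 has two. Change to 1 year uses ultracentrifugation values. Change to Day 120 uses Friedewald and Hopkins, with a baseline averaged over Visit 2 and the preceding screening visit. No rule names the LDL-C method, or a baseline to match it, for Visits 5 to 9, additional visits or the Last Visit.

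**The concern.** A change from baseline is interpretable only if both values come from the same method, or from methods known to agree. The SAP standardises the baseline and leaves the later follow-up value to whatever the protocol generates, which for a patient with TG below 400 mg/dL is a calculated LDL-C. Any systematic difference between calculated and ultracentrifugation LDL-C then enters the reported change at every visit from year 2 on.

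At stake is the long-term description of LDL-C within each arm, in a population enrolled for being at LDL-C goal on a statin. A reader of the by-visit table could take a step between year 1 and year 2 for a real change when only the method has changed.

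**Working it through.** The plan states no figure to reproduce, so the check is a visit-by-visit map of methods followed by an illustration of scale.

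**Step 1: method map for a patient with TG below 400 mg/dL and no missing values**

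| Visit | Follow-up LDL-C | Baseline LDL-C | Same method? |
|---|---|---|---|
| Visit 3 (Day 120) | Friedewald and Hopkins | Friedewald and Hopkins, averaged | Yes |
| Visit 4 (1 year) | Ultracentrifugation | Ultracentrifugation | Yes |
| Visits 5 to 9, additional visits, Last Visit | Friedewald or Hopkins | Ultracentrifugation (SAP 4.3.3) | No |

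If TG exceeds 400 mg/dL at a later visit, the follow-up value is Direct (not matched) or ultracentrifugation (matched). The documents do not give the share of patients below 400 mg/dL. The median baseline TG of 265 mg/dL in the 4 g/day arm of the sponsor's ANCHOR study (Protocol 1.2.2) suggests that most will be.

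**Step 2: the fallback at 1 year**

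The priority order is written for a missing value, with no condition that the other visit use the same method. A patient with ultracentrifugation at baseline but not at Visit 4 would have Direct LDL-C at Visit 4 set against ultracentrifugation at baseline. Direct LDL-C is scheduled at both visits, so a common method would usually exist.

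**Step 3: illustrative size of the within-arm shift**

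- Inputs from Protocol 1.2.2 (ANCHOR, 4 g/day): TG 265 mg/dL, LDL-C 82 mg/dL.
- Assumptions, not in the documents: calculated minus ultracentrifugation LDL-C = −g × TG; true LDL-C unchanged; control-arm TG unchanged.
- Spurious control-arm change (%) = −g × 265 / 82 × 100.

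| Assumed g | Gap (mg/dL) | Spurious change |
|---|---|---|
| 0.01 | −2.65 | −3.2% |
| 0.03 | −7.95 | −9.7% |
| 0.05 | −13.25 | −16.2% |
| −0.02 (opposite sign) | +5.3 | +6.5% |

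**Step 4: does matching the baseline change the between-arm difference?**

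Take g = 0.05 and a TG reduction of 20.1% on AMR101 (the medium-potency statin group in ANCHOR), so TG on AMR101 is 265 × 0.799 = 211.7 mg/dL.

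- Ultracentrifugation baseline: control −13.25, AMR101 −0.05 × 211.7 = −10.59; difference 2.66 mg/dL.
- Matched calculated baseline (82 − 13.25 = 68.75): control 0, AMR101 (82 − 10.59) − 68.75 = +2.66; difference 2.66 mg/dL.

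The between-arm difference is the same in mg/dL. As a percentage it goes from 2.66 / 82 = 3.2% to 2.66 / 68.75 = 3.9%. Matching removes the shift common to both arms and nothing else.

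**The case against.** **The mismatch is nowhere stated.** The LDL-C text in SAP 4.7.4 names two change analyses, 1 year and Day 120, and both are method-matched by default. The by-visit sentence is generic to all lipids and governs the summaries; the sentence on the Wilcoxon test names no visits. Hopkins LDL-C exists at every visit, so a single-method series could be used. This is fair as a description. But SAP 4.3.3 is a general rule for LDL-C baseline, and nothing exempts the later visits from it. A programmer who follows the text arrives at the mismatched comparison.

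**A reader might infer a bias against AMR101.** Friedewald LDL-C depends on TG, and the drug lowers TG. The documents do not support that inference as a consequence of the baseline rule. With baselines balanced by randomisation, a between-arm artefact comes from the follow-up method alone (Step 4). Its size and sign also rest on the assumed g: over g from −0.02 to 0.05 and TG reductions of 13.1% to 26%, it runs from −1.7 to +4.2 percentage points.

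**A reader might extend the point to RLP-C**, which is TC minus HDL-C minus LDL-C. The text does not support this. SAP 4.3.3 applies the ultracentrifugation baseline to LDL-C only. Other lipid parameters use the mean of Visit 2 and the preceding screening visit, and RLP-C is to be estimated from the standard panel, with no stated ultracentrifugation input.

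**The endpoints are exploratory.** SAP 4.3.6 says so, with testing at nominal 5%. That stands and limits the weight of the point.

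**Conclusion.** The point holds for the within-arm LDL-C change after Visit 4. Applied as written, SAP 4.3.3 and 4.7.4 set a calculated value against an ultracentrifugation baseline at Visits 5 to 9, additional visits and the Last Visit for patients with TG below 400 mg/dL. The fallback order can also mix methods at 1 year for a patient missing one ultracentrifugation value.

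The mismatch follows from reading the sections together and does not depend on any assumed figure. Its size does: the 3% to 16% range is an illustration under an assumed gap, and the true direction is unknown. For scale only, ANCHOR reported a placebo-adjusted LDL-C change of −6.2%; that is a between-arm figure and not directly comparable with a within-arm shift.

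The finding does not show a biased treatment comparison, and it does not reach the primary or secondary tests. The correction is still worth making before unblinding, because the rule as written gives a wrong within-arm change and the data for a right one are already collected.

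**What to change.** In SAP 4.3.3 and 4.7.4:

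1. Compute LDL-C change and percent change only between values from the same method.
2. Keep ultracentrifugation for 1 year versus baseline as the main LDL-C comparison.
3. For all other visits, use Hopkins LDL-C at both baseline and follow-up, with Friedewald-to-Friedewald as a sensitivity analysis. The Hopkins baseline already defined for Day 120 can be reused.
4. Where a fallback is needed, take the highest-priority method available at both visits.
5. Label later-visit results by method, because matching does not by itself remove a between-arm difference caused by a TG-dependent method at follow-up.

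The cost is SAP wording and programming; no new samples or assays are needed. A few patients with no common method will drop out of a given comparison, and their number should be reported.
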